## 11.8 Power for analysis of key secondary variables

Not applicable

### 11.9 Interim analyses

Commercially Confidential Information

# 12 Ethical considerations

# 12.1 Regulatory and ethical compliance

This clinical study was designed and shall be implemented, executed and reported in accordance with the ICH Harmonized Tripartite Guidelines for Good Clinical Practice, with applicable local regulations (including European Directive 2001/20/EC, US Code of Federal Regulations Title 21, and Japanese Ministry of Health, Labor, and Welfare), and with the ethical principles laid down in the Declaration of Helsinki.

# 12.2 Responsibilities of the investigator and IRB/IEC

Before initiating a trial, the investigator/institution must obtain approval/favorable opinion from the Institutional Review Board/Independent Ethics Committee (IRB/IEC) for the trial protocol, written informed consent form, consent form updates, subject recruitment procedures (e.g. advertisements) and any other written information to be provided to subjects. Prior to study

start, the investigator is required to sign a protocol signature page confirming his/her agreement to conduct the study in accordance with these documents and all of the instructions and procedures found in this protocol and to give access to all relevant data and records to Novartis monitors, auditors, Novartis Quality Assurance representatives, designated agents of Novartis, IRBs/IECs, and regulatory authorities as required. If an inspection of the clinical site is requested by a regulatory authority, the investigator must inform Novartis immediately that this request has been made.

Confidential

For multi-center trials, a Coordinating Investigator will be selected by Novartis by the time of Last Patient Last Visit to be a reviewer and signatory for the clinical study report.

# 12.3 Publication of study protocol and results

The key design elements of this protocol will be posted in a publicly accessible database such as clinicaltrials.gov. In addition, upon study completion and finalization of the study report the results of this trial will be either submitted for publication and/or posted in a publicly accessible database of clinical trial results.

# 12.4 Quality Control and Quality Assurance

Novartis maintains a robust Quality Management (QM) system that includes all activities involved in quality assurance and quality control, including the assignment of roles and responsibilities, the reporting of results, and the documentation of actions and escalation of issues identified during the review of quality metrics, incidents, audits and inspections.

Audits of investigator sites, vendors, and Novartis systems are performed or overseen by Novartis Pharma Auditing and Compliance Quality Assurance (or CRO working on behalf of Novartis), a group independent from those involved in conducting, monitoring or performing quality control of the clinical trial. The clinical audit process uses a knowledge/risk based approach.

Audits are conducted to assess GCP compliance with global and local regulatory requirements, protocols and internal SOPs, and are performed according to written Novartis processes.

# 13 Protocol adherence

This protocol defines the study objectives, the study procedures and the data to be collected on study participants. Additional assessments required to ensure safety of subjects should be administered as deemed necessary on a case by case basis. Under no circumstances is an investigator allowed to collect additional data or conduct any additional procedures for any research related purpose involving any investigational drugs under the protocol.

Investigators agree they will apply due diligence to avoid protocol deviations. If an investigator feels a protocol deviation would improve the conduct of the study this must be considered a protocol amendment, and unless such an amendment is agreed upon by Novartis and approved by the IRB/IEC and health authorities, where required, it cannot be implemented.

## **13.1 Protocol Amendments**

Any change to the protocol can only be made in a written protocol amendment that must be approved by Novartis, Health Authorities where required, and the IRB/IEC prior to implementation.

Amendments that are intended to eliminate an apparent immediate hazard to subjects may be implemented immediately, provided the Health Authorities are subsequently notified by protocol amendment and the reviewing IRB/IEC is notified.

Notwithstanding the need for approval of formal protocol amendments, the investigator is expected to take any immediate action required for the safety of any subject included in this study, even if this action represents a deviation from the protocol. In such cases, the reporting requirements identified in Section 9 (Safety Monitoring) must be followed and the Study Lead informed.

# 15 Appendix 1: Liver Event Definitions and Follow-up Requirements

Definition	Thresholds
Potential Hy's law cases	
 
ALT or AST > 3 × ULN and TBL > 2 × ULN without initial increase in ALP to > 2 × ULN
 

ALT or AST elevation with coagulopathy	
 
ALT or AST > 3 × ULN and INR > 1.5 (in the absence of anticoagulation)
 

ALT or AST elevation accompanied by symptoms	
 
ALT or AST > 3 × ULN accompanied by (general) malaise, fatigue, abdominal pain, nausea, or vomiting, or rash, or eosinophilia
 

Isolated ALT or AST elevation	• ALT or AST > 8 × ULN
	• $5 \times ULN < ALT/AST \le 8 \times ULN$
	• $3 \times ULN < ALT/AST \le 5 \times ULN$
Isolated ALP elevation	
 
ALP > 2 × ULN (in the absence of known bone pathology)
 

Others	Any clinical event of jaundice (or equivalent term)
	Any adverse event potentially indicative of liver toxicity

Criteria	Actions required
Potential Hy's Law case ALT or AST elevation with coagulopathy ALT or AST elevation accompanied by symptoms Isolated ALT or AST elevation > 8 × ULN Jaundice	
 
Discontinue the study treatment immediately
 
Hospitalize, if clinically appropriate
 
Establish causality
 
Complete CRFs per liver event guidance*
 

Isolated ALT or AST elevation > 5 to ≤ 8 × ULN	
 
If confirmed, consider interruption or discontinuation o study drug
 

	
 
If elevation persists for more than 2 weeks, discontinue the study drug
 

	Establish causality
	
 
Complete CRFs per liver event guidance*
 

Isolated ALT or AST elevation > 3 to ≤ 5 × ULN (patient is asymptomatic)	Monitor liver chemistry tests two or three times weekly
Isolated ALP elevation	Repeat liver chemistry tests within 48-72 hours
	
 
If elevation is confirmed, measure fractionated ALP; if >50% is of liver origin, establish hepatic causality
 

	Complete CRFs per liver event guidance*
Any AE potentially indicative of liver toxicity	
 
Consider study treatment interruption or discontinuation
 

	Hospitalize if clinically appropriate
	
 
Complete CRFs per liver event guidance*
 

\*Liver event guidance for CRF completion is available in the Site Operations Manual

Disease	Assessment
Hepatitis A, B, C, E	
 
IgM anti-HAV; HBSAg, IgM anti-HBc, HBV DNA; anti- HCV, HCV RNA, IgM & IgG anti-HEV, HEV RNA
 

CMV, HSV, EBV infection	
 
IgM & IgG anti-CMV, IgM & IgG anti-HSV; IgM & IgG anti-EBV
 

Autoimmune hepatitis	
 
ANA & ASMA titers, total IgM, IgG, IgE, IgA
 

Alcoholic hepatitis	• Ethanol history, GGT, MCV, CD-transferrin
Nonalcoholic steatohepatitis	Ultrasound or MRI
Hypoxic/ischemic hepatopathy	
 
Medical history: acute or chronic CHF, hypotension, hypoxia, hepatic venous occlusion. Ultrasound or MRI.
 

Biliary tract disease	Ultrasound or MRI, ERCP as appropriate.
Wilson disease	Caeruloplasmin
Hemochromatosis	Ferritin, transferrin
Alpha-1-antitrypsin deficiency	Alpha-1-antitrypsin

#### Table 15-3Exclusion of underlying liver disease

# 16 Appendix 2: Specific Renal Alert Criteria and Actions

#### Table 16-1 Specific Renal Alert Criteria and Actions

Renal Event	Actions	
Confirmed serum creatinine increase 25 – 49%	

Consider causes and possible interventions

Follow up within 2-5 days

	
Serum creatinine increase  50 % + OR if <18 years old, eGFR < 35 mL/min/1.73 m 	
 
Consider causes and possible interventions
 
Repeat assessment within 24-48h if possible
 
Consider drug interruption or discontinuation
 
	
	

unless other causes are diagnosed and corrected

Consider patient hospitalization and

	
New onset dipstick proteinuria ≥ 3+ OR	
 
specialized treatment
 
Consider causes and possible interventions
 
Assess serum albumin & serum total protein
 
	
Protein-creatinine ratio (PCR) ≥ 1g/g Cr (or mg/mmol equivalent as converted by the measuring laboratory)	
 
Repeat assessment to confirm
 
Consider drug interruption or discontinuation unless other causes are diagnosed and corrected
 
	
New onset hematuria ≥ 3+ on urine dipstick	
 
Assess & document
 
Repeat assessment to confirm
 
Distinguish hemoglobinuria from hematuria
 
Urine sediment microscopy
 
Assess sCr
 
Exclude infection, trauma, bleeding from the distal urinary tract/bladder, menstruation
 
Consider bleeding disorder
 
	

+Corresponds to KDIGO criteria for Acute Kidney Injury

Additional specialized assessments are available to assess renal function or renal pathology. (Note: In exceptional cases, when a nephrologist considers a renal biopsy, it is recommended to make slide specimen available for evaluation by the RSG to potentially identify project-wide patterns of nephrotoxicity.)

Whenever a renal event is identified, a detailed patient history and examination are indicated to identify and potentially eliminate risk factors that may have initiated or contributed to the event:

- Blood pressure assessment (after 5-minute rest, with an appropriate cuff size)
- Signs and symptoms like fever, headache, shortness of breath, back or abdominal pain, dysuria or hematuria, dependent or periorbital edema
- Changes in blood pressure, body weight, fluid intake, voiding pattern, or urine output
- Concomitant events or procedures such as trauma, surgical procedures, cardiac or hepatic failure, contrast media or other known nephrotoxin administration, or other diseases or causes, e.g., dehydration due to delirium, tumor lysis

#### Table 16-2Renal Event Follow Up

#### FOLLOW-UP OF RENAL EVENTS

Assess, document and record in CRF

- Urine dipstick and sediment microscopy evidence of DIN: crystals, red blood cells (dysmorphic/glomerular vs. non-dysmorphic/non-glomerular), white blood cells, tubular epithelial cells
- Blood pressure and body weight
- Serum creatinine, BUN, electrolytes (sodium, potassium, phosphate, calcium), bicarbonate and uric acid
- Urine output

Review and record possible contributing factors to the renal event (co-medications, other co-morbid conditions) and additional diagnostic procedures (MRI etc.) in the CRF

Monitor patient regularly (frequency at investigator's discretion) until -

- Event resolution: (sCr within 10% of baseline or PCR < 1 g/g Cr, or ACR <300 mg/g Cr) or
- Event stabilization: sCr level with ±10% variability over last 6 months or protein-creatinine ratio stabilization at a new level with ±50% variability over last 6 months.
- Analysis of urine markers in samples collected over the course of the DIN event

# 17 Appendix 3: Relative Potencies of Glucocorticoids

Equivalent Potency (mg)⁺
25
20
5
5
4
4
0.6
0.75

#### Table 17-1 Steroid Equivalents

+ Modified from (Hwang et al 2017).

1.1 Scope of document

The RAP documents contain detailed information to aid the production of Statistics & Programming input into the Clinical Study Report (CSR) for trial "CCM389X2201".

The Statistical analysis plan (SAP) describes the implementation of the statistical analysis planned in the protocol.

Tables, Figures, Listings (TFL) details the presentation of the data, including shells of summary tables, figures and listings, and Programming Datasets Specification (PDS) contains programming specifications e.g. for derived variables and derived datasets, to support the creation of CSR outputs.

1.2 Study reference documentation

To assess the impact of CMK389 on a

composite index of pulmonary

physiology and exercise capacity

To explore the impact of CMK389

tomography/computed tomography ([18F]FDG-PET/CT) imaging

positron emission

observed with [18F]-fluorodeoxyglucose

This Statistical Analysis plan is based on the Amendment 8 of the study protocol (dated: 23Jun2022).

1.3 Study objectives

1.3.1. Primary objective(s)

Primary objective(s)	Endpoints related to primary objectives		
To assess the efficacy of CMK389 in subjects with chronic pulmonary sarcoidosis	Change in forced vital capacity, % of predicted, (FVC%) between baseline and Week 16, between CMK389 and placebo.		
1.3.2. Secondary objective(s)			
Secondary objective(s)	Endpoints related to secondary objective(s)		
 To assess the impact of CMK389 on steroid use (mg days) 	Difference in steroid usage for each arm of the study between baseline and end		

of treatment.

Proportion of patients who deteriorate

from baseline to Week 16, defined as:

parameters (SUVmax and SUVmean)

relative reduction in FVC \geq 10% or relative reduction if FEV1 \geq 10% or relative reduction of DLCO \geq 15% or relative reduction of 6MWD \geq 50 m.

Change in [18F]FDG-PET/CT

between baseline and Week 16.

To assess the pharmacokinetics of CMK389	Pharmacokinetic parameters (Cmax/End of infusion, Ctrough) of CMK389.
• To assess the safety and tolerability of CMK389	Adverse events, vital signs and routine safety laboratory results.
To assess the impact of CMK389 on pulmonary physiology	Change in forced expiratory volume in one second (FEV1) and diffusion capacity for carbon monoxide (DLCO) between baseline and Week 16.
To assess the impact of CMK389 on exercise capacity	Change in 6-minute walk distance (6MWD) between baseline and Week 16.

1.3.3. Exploratory objective(s)

[figure not shown]
Commercially Confidential Information

1.4 Study design and treatment

This is a subject and investigator-blinded, randomized, placebo-controlled, parallel group, repeat-dose, multicenter, non-confirmatory study of the safety and efficacy of CMK389 administered intravenously every 4 weeks for a total of 4 doses in chronic pulmonary sarcoidosis patients.

Approximately 66 patients will be randomized in a 1:1 ratio to receive either CMK389 or placebo. Randomization will be stratified by prior sarcoidosis immunosuppressant therapy (azathioprine or methotrexate). The expected total duration of participation for men and women of non-child bearing potential is approximately 38 weeks. For women of childbearing potential, the expected duration of participation is approximately 62 weeks.

Figure 1-1: Study design scheme

2 First interpretable results (FIR)

3 Interim analyses

Commercially Confidential Information

4 Statistical methods: Analysis sets

For all analysis sets, subjects will be analyzed according to the study treatment(s) received. In case(s) of miss-stratification, the real stratum will be used in the analysis.

The safety analysis set will include all subjects that received any study drug.

The PK analysis set will include all subjects with at least one available valid (i.e. not flagged for exclusion) PK concentration measurement, who received any study drug and with no protocol deviations with relevant impact on PK data.

The PD analysis set will include all subjects with available PD data and no protocol deviations with relevant impact on PD data. Also, data collected after a change of the background therapy not based on the CSE algorithm (see Section 3.1 of protocol) will be excluded from the analysis set if assessed as having a potentially relevant impact on PD data.

Table 4-1 Protocol deviation codes and analysis sets

Category Deviation code	Text description of deviation	Data exclusion
Subjects are excluded from all case of these PDs:	(safety) analysis in	Exclude subject completely from all (safety) analysis sets
INCL01	Deviation from inclusion criteria: Written informed consent was not obtained before any study assessment was performed	Yes
Subjects are excluded from Phthese PDs:	Canalysis in case of	Exclude subject from PK analysis set
INCL01	Deviation from inclusion criteria: Written informed consent was not obtained before any study assessment was performed	Yes

Subjects are excluded from PI these PDs:	Exclude subject from PD analysis set	
INCL01	Deviation from inclusion criteria: Written informed consent was not obtained before any study assessment was performed	Yes
TRT01	Treatment deviation with impact on PD data	Yes
TRT02	Treatment deviation with impact on PD data from a timepoint onwards	Yes from a timepoint onwards
OTH01	Other deviation with impact on PD data	Yes
OTH02	Other deviation with impact on PD data from a timepoint onwards	Yes, from a timepoint onwards

Category Deviation code	Text description of deviation	Data exclusion
OTH04	Impact on spirometry and DLCO at a specific time point	Yes, at a specific timepoint only.
OTH12	Impact on spirometry at a specific time point	Yes, at a specific timepoint only.
OTH13	Impact on DLCO at a specific time point	Yes, at a specific timepoint only.
CMD02	Prohibited concomitant medication used with a relevant impact on efficacy endpoint	Yes, from a timepoint onwards
INCL04	Deviation from inclusion criteria: No biopsy proven pulmonary sarcoidosis diagnosed > 1 year prior to screening	Yes
INCL06	Deviation from inclusion criteria: HRCT <= 15% reticular volume at screening	Yes
EXCL05	Deviation from exclusion criteria: FVC < 50% at screening	Yes
EXCL06	Deviation from exclusion criteria: mMRC dyspnea scale >= 3 at screening	Yes
EXCL27	Deviation from exclusion criteria: deteriorated during Run-in	Yes

If updates to this table are needed, an amendment to the SAP needs to be implemented prior to DBL.

All DLCO related parameters will be excluded at specific visit only if the condition below is encountered: DLCO % change (absolute value) vs previous assessment > 35% or % change in alveolar volume vs previous assessment > 20%.

DLCO related parameters are: DLCO (absolute value and % predicted), ALVVOL (alveolar volume), DLCOHCCP (corrected by Hg), DLCOVA (/ volume), CPID (CPI = it includes DLCO).

5 Statistical methods for Pharmacokinetic (PK) parameters

All subjects within the PK analysis set will be included in the PK data analysis.

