### Treatment Epoch

A 16-week treatment epoch will commence on Day 1. Patients with a CSD of "deteriorating" at this visit will be ineligible to continue in the study. Patients with a CSD of "improved" or "stable" will decrease steroid dose by 1-step. (Note: Steroids will not be tapered below 2.5 mg/day) Then, the patients will be randomized to receive CMK389 or placebo, stratified by prior sarcoidosis immunosuppressant therapy (Stratum 1: azathioprine or Stratum 2: methotrexate).

During the treatment epoch, steroid dose will be guided by the results of CSE/CSD (Figure 3-3). During the treatment epoch, adverse events will be monitored on an ongoing basis. Monthly visits are scheduled to assess safety and efficacy. Physical exam, vital signs, blood draw (safety labs, pharmacokinetic [PK] samples, CCI ), spirometry, 6MWT, mMRC and CCI will be performed during the treatment epoch every 4 weeks or as described in the Assessment Schedule (Table 8-1).

Every effort should be put in place to adhere to this algorithm, but in cases where the Investigator feels that, during the Treatment Epoch, a subject's increase in steroids outside of the specified incremental dose-steps indicated or re-initiation of methotrexate or azathioprine is clinically indicated, this therapy can be started/adjusted. All the actual treatments should be reported in the CRF and all the PD parameters collected after therapy adjustment will be excluded from the primary analysis.

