## 6.11 Concomitant treatment

All prescription medications, over-the-counter drugs and significant non-drug therapies (including physical therapy and blood transfusions) administered or taken within the timeframe defined in the entry criteria prior to the start of the study and during the study, must be recorded on the Concomitant medications/Significant non-drug therapies section of the CRF.

Medication entries should be specific to trade name, the single dose and unit, the frequency and route of administration, the start and discontinuation date and the reason for therapy.

Each concomitant drug must be individually assessed against all exclusion criteria/prohibited medication. If in doubt, the investigator should contact Novartis before randomizing a subject or, if the subject is already enrolled, to determine if the subject should continue participation in the study.

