# **11.7** Sample size calculation

We assume around 15% drop out, which should provide FVC data at week 16 from 56 patients (approximately 28 in each arm), if approximately 66 patients are randomized. Commercially Confidential Information

The sample size is determined by calculations with respect to the Bayesian analyses (Fisch et al 2014); based on uninformative priors) of the change from baseline in the percent predicted FVC after 16 weeks of treatment. This was derived via simulations using the QTD software. With 28 patients per group providing data at week 16 and assuming a standard deviation of 9% (Judson et al 2014), there is approximately 80% power to meet the efficacy criterion (posterior probability that CMK389 is better than placebo  $\geq 90\%$ ), if the true effect of CMK389 over placebo is 5%. Furthermore there is 10% probability of meeting the efficacy criterion if the true treatment difference is 0% (type I error rate).

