6.1.5 Sensitivity/Supplementary analyses

Supplementary analyses may be conducted including also FVC values collected after a change of the background therapy driven by the algorithm or not.

Finally the analysis may be repeated excluding the observations with flags related to data quality (REIRESFL='Y').

A scatterplot will be produced to investigate the relationship between week 16 FVC changes from baseline and SUV max % changes

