6.2 Secondary objectives

6.2.1 Variables

Secondary variables for this study are:

- Steroid use (mg days): Change from baseline in steroid usage as determined by the investigator's decision (for any reason algorithm mediated or just related to an investigator's decision).
- - Dose for subjects dosed with Methylprednisolone steroid doses of 4, 6, 8, 10 mg will be multiplied by 1.25 to become Prednisolone equivalent.
- Composite index of pulmonary physiology and exercise capacity: Subject who deteriorates from baseline to each visit/Week 16, is defined as a subject with:
 - o relative reduction if FVC \geq 10%, or
 - o relative reduction if FEV1 \geq 10%, or

- o relative reduction of DLCO \geq 15%, or
- o relative reduction of 6MWD \geq 50 m.
- [18F]FDG-PET/CT: Percent change from baseline in SUVmax and SUVmean
- Pulmonary function tests: Change from baseline in FVC (L), FEV1 (L and % predicted), FEV1/FVC, PEF and DLCO (absolute values and % predicted). DLCO expressed as % predicted and adjusted for Hemoglobin will be derived by the vendor as described in: Graham et others 2017. A composite physiological index (CPI) will be derived too following this formula: CPI = 91 0.65*DLCO(%) 0.53*FVC(%) + 0.34*FEV1(%)
- 6MWD: Change from baseline in distance walked and for the distance saturation product. The latter will be derived as the product between the distance walked and lowest oxygen saturation (SpO2%) value observed during the test, that is to say the lowest of the values taken after 1,2,3,4,5,6 Minutes from the start of the test (Lettieri 2006).
- IL-18 and IL-18bp concentrations

The direction of benefit is as follows

- an increase in values is beneficial for: absolute FVC, FEV1, PEF, DLCO and 6MWD.
- A decrease in values is beneficial for: [18F]FDG-PET/CT (SUVmax and SUVmean).

[18F]FDG-PET/CT

The [18F]FDG-PET/CT imaging data will be analyzed by the vendor to identify the standardized uptake values in the following categories:

- A maximum of 10 focal nodal uptake regions (mediastinal, hilar)
- A maximum of 10 focal regions of uptake in lung parenchyma
- A maximum of 10 extra-thoracic focal uptake regions on the whole body scan

[18F]FDG-PET/CT mean uptake in the reference tissue:

- Lung parenchyma, unaffected by focal lesion uptake
- Ascending aorta blood pool

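### Removing data after off-algorithm therapy changes can delete outcome-dependent events from the deterioration composite, which has no rule for missing status

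*SAP*

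**What the plan says.** Protocol 3.1 (Treatment Epoch) lets the investigator depart from the steroid steps, or restart methotrexate or azathioprine, when clinically indicated. The consequence for analysis is stated in several places, and the scopes differ:

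- Protocol 3.1: "all the PD parameters collected after therapy adjustment will be excluded from the primary analysis".
- SAP section 4: "data collected after a change of the background therapy not based on the CSE algorithm (see Section 3.1 of protocol) will be excluded", on condition that a relevant impact on PD is judged possible. Protocol 11.1 has the same conditional rule. It is not limited to the primary analysis, and the opening of SAP section 6 applies the PD set to all PD analyses.
- SAP 6.1.1: for the main efficacy analysis, data after an off-algorithm steroid increase are excluded without that condition, either at one visit or from a time point onwards. Methotrexate and azathioprine are not mentioned.

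The composite is defined in SAP 6.2.1: "Composite index of pulmonary physiology and exercise capacity: Subject who deteriorates from baseline to each visit/Week 16, is defined as a subject with" a threshold fall in FVC, FEV1, DLCO or 6MWD. No therapy change counts. Its timing also varies. Protocol 2.2 and 11.5.1 and SAP 1.3.2 use Week 16, SAP 6.2.2 tabulates Weeks 4, 8, 12 and 16, and the logistic model in SAP 6.2.3 takes any deterioration in the treatment period.

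For restoring the excluded data, SAP 6.1.5 offers: "Supplementary analyses may be conducted including also FVC values collected after a change of the background therapy driven by the algorithm or not".

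**The concern.** An off-algorithm change may be made because the patient is getting worse. If the data after it are then removed, a patient who deteriorated can be left without a qualifying value. That patient either leaves the denominator or, if absence of a recorded event is read as no event, is counted as stable. The plan does not say which.

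The repeated-measures model for FVC has a missing-at-random provision (Protocol 11.4.3, SAP 6.1.3.1). The logistic model for the composite has no such step: it adjusts only for baseline steroid dose, treatment and prior immunosuppressant, none of which carries the worsening that led to the change. The supplementary analysis that restores post-change data names FVC. The permission to repeat the primary's sensitivity analyses appears in SAP 6.2.3 under PET/CT and under lung function and 6MWD, not under the composite.

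At stake is a secondary objective. The deterioration rate would tend to be too low, and the arms would look more alike if such changes are commoner on placebo.

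**Working it through.** **The plan's own figure.** Inputs: "Approximately 66 patients will be randomized in a 1:1 ratio to receive either CMK389 or placebo" (SAP 1.4); about 15% drop-out, "With 28 patients per group providing data at week 16 and assuming a standard deviation of 9" points, and power stated "if the true effect of CMK389 over placebo is 5" points (Protocol 11.7). Then 66 × 0.85 = 56.1, or 28 per arm. SE = 9 × √(2/28) = 2.405; 5/2.405 = 2.079; one-sided 10% critical value 1.282; power = Φ(2.079 − 1.282) = 0.787, against a stated figure of about 80%. The primary design reproduces and this point does not affect it. For secondary variables Protocol 11.8 gives no power, and no composite event rate or frequency of off-algorithm changes is stated anywhere. All rates below are assumptions.

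**Who loses status.**
- *Week 16 definition:* every patient whose data are excluded from the change through Week 16.
- *Any-visit model (SAP 6.2.3):* only patients with no qualifying FVC, FEV1, DLCO or 6MWD value at or before the change. At scheduled visits the clinical status evaluation precedes steroid titration (Protocol 3.1 and 8.5.5), so a fall recorded at that visit stays in. The exposed cases are changes between visits, or changes prompted by symptoms before a threshold was crossed.

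**Size by share of deteriorators affected.** Let p be the true deterioration rate in an arm and f the share of deteriorators left with no retained event, the same f in both arms. If they are dropped, the observed rate is p(1 − f)/(1 − pf); if scored as non-events, p(1 − f). Power uses 33 per arm (66/2), one-sided 10%, with the pooled-variance normal approximation. At f = 0 and 40% v 20%: SE0 = √(2 × 0.3 × 0.7/33) = 0.1128, SE1 = √((0.24 + 0.16)/33) = 0.1101, power = Φ((0.20 − 1.282 × 0.1128)/0.1101) = 0.69.

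| Assumed truth | f | Dropped: rates, difference, power | Non-events: difference, power |
|---|---|---|---|
| 40% v 20% | 0 | 20.0 points, 0.69 | 20.0 points, 0.69 |
| 40% v 20% | 0.10 | 37.5% v 18.4%, 19.1 points, 0.67 | 18.0 points, 0.65 |
| 40% v 20% | 0.25 | 33.3% v 15.8%, 17.5 points, 0.63 | 15.0 points, 0.57 |
| 40% v 20% | 0.50 | 25.0% v 11.1%, 13.9 points, 0.53 | 10.0 points, 0.44 |
| 30% v 15% | 0 | 15.0 points, 0.57 | 15.0 points, 0.57 |
| 30% v 15% | 0.25 | 24.3% v 11.7%, 12.6 points, 0.51 | 11.2 points, 0.47 |
| 30% v 15% | 0.50 | 17.6% v 8.1%, 9.5 points, 0.43 | 7.5 points, 0.37 |

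**Size by counts.** Assume 28 evaluable per arm and true deteriorators 9 on placebo and 4 on CMK389: 9/28 − 4/28 = 17.9 points.
- Events lost 4 and 1: 5/24 − 3/27 = 9.7 points (dropped); 5/28 − 3/28 = 7.1 (non-events).
- Lost 2 and 0: 7/26 − 4/28 = 12.6; 7/28 − 4/28 = 10.7.
- Lost 2 and 2: 7/26 − 2/26 = 19.2; 7/28 − 2/28 = 17.9.
- Lost 0 and 2: 9/28 − 2/26 = 24.5; 9/28 − 2/28 = 25.0.

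An equal share shrinks the difference because it removes more events from the arm with more. Equal counts barely move it, and heavier loss on CMK389 widens it.

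**The 20% condition.** Protocol 11.5.1 runs the regression only if at least 20% of subjects have the event. With 14/66 = 21.2%, losing two gives 12/64 = 18.8% (dropped) or 12/66 = 18.2% (non-events). With 16/66 = 24.2%, losing four and dropping them gives 12/62 = 19.4%. In these cases the planned model would not be fitted.

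**The case against.** The strongest reply is that few patients are affected. Algorithm-driven increases keep all their data; off-algorithm changes are meant to be exceptions; and exclusion under SAP section 4 needs a judgement of relevance. SAP 6.2.3 models any deterioration in the treatment period, so events seen at or before the change still count. The composite's 10% FVC and FEV1 limits are also tighter than the 15% used for a worse rating in Protocol Figure 3-2 (the reference days differ), so it may trigger sooner. Steroid increases for any reason are tabulated and modelled separately. The endpoint is unpowered, in a non-confirmatory study judged on FVC.

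Most of this stands, and it limits the point. A reader might infer that patients leave the analysis set, or that the composite is answered without its clearest events. Neither follows: the rule removes later data, and the any-visit model keeps earlier events. Nor is the objective estimated only in patients who needed no off-algorithm treatment.

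Three things remain. The Week 16 endpoint, which is the one the objectives tables name, does lose these patients' status. The separate regression mixes algorithm-driven with off-algorithm steroid increases and misses a methotrexate or azathioprine restart on its own. And missing composite status has no scoring rule under either definition.

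**Conclusion.** The point holds in a limited form and is worth a cheap correction. A stated rule removes data from a binary endpoint for a reason that can depend on the outcome, and the plan neither handles nor restores it. The reach is full under the Week 16 definition and partial under the any-visit model.

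It would be tempting to say that deterioration is understated in both arms and the treatment difference always shrinks. The documents do not support that. With losses of 2 and 0 one arm is untouched; with 2 and 2 the difference stays at 17.9 or rises to 19.2 points; with 0 and 2 it widens. Shrinkage requires that the lost events fall more on placebo, which is plausible if CMK389 works but not known. The calculations also assume that every affected patient is a true deteriorator with no retained event. Under the any-visit model that is the worst case for patients with an excluded change.

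**What to change.** In SAP 6.2.1 and 6.2.3:

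1. State one time definition for the composite, reconciling Week 16 with any visit during treatment.
2. Do not apply the section 4 post-change exclusion to the composite, and reconcile the scope of that rule across Protocol 3.1, SAP section 4 and SAP 6.1.1. Protocol 11.1 has the section 4 rule too, so the exemption should be recorded there or as a stated departure.
3. Keep the threshold-only composite as the protocol defines it. Beside it, report a version that also counts as deterioration an off-algorithm steroid increase, or a methotrexate or azathioprine restart, recorded as being for worsening sarcoidosis before the V299 assessments. This is useful even with item 2, because a Week 16 value retained after added therapy may no longer show the fall.
4. State how any remaining missing status is scored.

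The cost is a few SAP sentences and one derived flag. Protocol 6.11 already collects "the start and discontinuation date and the reason for therapy", and SAP 6.1.1 already plans to identify off-algorithm steroid increases by program and manual check; restarts would need the same check. The added version has drawbacks: it includes a blinded investigator's treatment decision, may pick up extrapulmonary worsening, and overlaps the steroid-increase endpoint. It therefore belongs beside the protocol's composite and should not replace it. No change to patient management is proposed.
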